relapses occur within the first few weeks of abstinence[19], this can be improved by recruiting quitters who have just quit, and starting the WhatsApp groups as soon as possible. Second, the intervention content and dosage through social media needs to be revised to increase participation. For instance, only 6 out of the 16 participants, who reported relapse at 2-month, shared their relapse experience in the group. The few number of reports of relapse posed barriers for early intervention. Due to limited number of eligible participants, some groups had only 2 to 5 participants, which led to inactive discussion. About one-fourth of the participants only stayed in the group, but did not post anything. These findings highlighted the importance of skilful and theory-driven group moderation, and inclusion of more updated and interesting content to increase the level of participation. Lastly, for a larger RCT, we shall add more recruitment sites to increase participant recruitment and generalizability. A subsequent cost-effectiveness analysis based on trial data will establish the optimal balance between costs and health effectiveness outcomes, and provide health economic data to policymakers to facilitate informed decision-making of health interventions for tobacco control

c) Aims and Hypotheses to be Tested:

This study aims to examine the effectiveness and cost-effectiveness of WhatsApp group discussion for smoking relapse prevention. To assess the effect due to treatment modality through the WhatsApp social group, we will analyse the frequency and topics of the posts in each social group and in each participant. The primary hypothesis is whether quitters who participate in the WhatsApp group discussion will have a higher prevalence of validated tobacco abstinence at 12-month follow-up than those who do not. Our second hypothesis is that greater participation in the social groups, indicated by number of posts received, posted and/or viewed, was associated with higher likelihood to quit at 12-month. The third hypothesis is that the WhatsApp intervention for a recent quitter is a more cost-effective option for tobacco abstinence and prolonged survival when compared to the control group.

d) Plan of Investigation:

(i) Subjects

Inclusion criteria:

- Smoke at least 1 cigarette per day at the service intake
- Aged 18 years or above
- Have enrolled or re-enrolled in the smoking cessation treatment for no more than 8 weeks
- No smoking for 7 to 14 days

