- Able to communicate in Cantonese/Mandarin and read Chinese
- Have a smart phone with local network connection

Exclusion criteria:

- Have unstable physical or psychological conditions as advised by doctors or counsellor in charge
- Have become pregnant in the past 2 months

The fourth criterion will be used because our proposed RCT will target the quitters who have recently quit, and exclude those who will have maintained a longer period of abstinence. Our pilot RCT showed that 10 participants on average could be recruited in 8 clinics each week[16]. Our proposed RCT with 30 clinics of the 3 major service providers of smoking cessation, and recruiting quitters who have quit for 7 to 30 days will recruit 25 to 35 participants each week.

Sample size calculation

Our pilot RCT showed that the OR of the CO validated quit rates between the intervention and

control group was 2.04 (95%CI 0.74-5.65) (Intervention: 26.0%, Control: 15.0%)[16]. Because our proposed RCT will recruit quitters who have recently quit, we have conservatively estimated that the OR will be 1.70 (23.0% vs 15.0%). To detect a significant difference of quit rate with 2-tailed z-test by *GPower 3.1* between the two groups with a power of 90% (to reduce type II error) and 5% significant level (type I error), we will need 1,008 participants in total (504 participants per group).

(ii) Methods

Design

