The primary outcome is biochemically validated (exhaled carbon monoxide < 4ppm; or/and saliva cotinine < 10ng/ml) tobacco abstinence at 12-month follow-up, which have been confirmed as a stringent criterion for abstinence verification for quitters who use nicotine replacement therapy^[21]. Secondary outcomes include prevalence of self-reported 7-day and continuous abstinence over the study period, and relapse rate, which is defined as the proportion of quitters who smoke at least 5 cigarettes in 3 consecutive days over the study period. Ancillary outcomes include change in frequency and intensity of smoking urge, change in the Minnesota Nicotine Withdrawal Scale (MNWS), and the change in HRQOL measured by Short-form 6-item instrument and EuroQoL 5-dimension 5-level (EQ-5D-5L) health utility scores from baseline to follow-ups. For cost-effectiveness analysis, the outcomes are the incremental cost-effectiveness ratio (ICER) in terms of cost per an additional tobacco abstinence gained for intervention compared to control group, and the ICER in terms of cost per life-years gain or quality-adjusted life-years gained for intervention versus control group.

(iii) Study design A pragmatic open-labelled 2-arm randomized controlled trial

(iv) Data processing and analysis

Statistical analysis

By intention-to-treat analysis (in line with CONSORT guideline), participants who are lost or refuse the follow-up will be treated as smokers with no changes in daily cigarette consumption. The analysis with multiple imputation (MI) procedure to impute the missing exhaled CO will be conducted as sensitivity analysis. Considering the correlated outcomes of participants within the same WhatsApp group, a post-hoc analysis by generalized estimating equation (GEE) model will be used to summarise the intervention effect with the odds ratios, with and without adjustment for baseline characteristics. Number needed to treat (NNT), which shows the number of treated subjects needed to have one additional quitter at 12-month, will be computed by taking the reciprocal of the risk difference between the 2 RCT groups. Number of posts received, posted or/and viewed in each participant and in each social group will be documented, and then included in the final GEE model to assess their association with the cessation outcome.

Text mining of the WhatsApp groups

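### Coding lost and refusing participants as smokers may inflate the participation–abstinence association of hypothesis 2, and the planned imputation is not linked to that model

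*Combined protocol and SAP*

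**What the plan says.** Section c) (Aims and Hypotheses) states as the second hypothesis that "greater participation in the social groups, indicated by number of posts received, posted and/or viewed, was associated with higher likelihood to quit at 12-month".

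Section d)(iv), Statistical analysis, gives one rule for missing outcomes, under intention to treat: "participants who are lost or refuse the follow-up will be treated as smokers with no changes in daily cigarette consumption". Later in the same paragraph, the post counts are to be "included in the final GEE model to assess their association with the cessation outcome". No separate missing-data rule is given for that model, and the text does not say whether the cessation outcome is the validated or the self-reported one.

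Three other statements bear on this:

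- Section d)(ii), Outcomes, makes biochemically validated 12-month abstinence primary. Self-reported 7-day abstinence is secondary.
- Section d)(ii), Follow-up, offers the breath or saliva test only to those who report 7-day abstinence by telephone, at a place they choose.
- Section d)(iv) plans multiple imputation of missing exhaled carbon monoxide as a sensitivity analysis. It names no imputation variables and does not connect this to the participation model.

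On the pilot, section b) reports: "About one-fourth of the participants only stayed in the group, but did not post anything".

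**The concern.** Randomisation does not protect a comparison of active with silent members. To be recorded as a validated quitter, a member must answer the 12-month call and then give a sample. Someone who never engaged with the group may be less willing to do either. The coding turns that reluctance into smoking. Two equally abstinent members could then be recorded differently because one was easier to reach, and the error runs in the direction hypothesis 2 predicts.

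A positive result would naturally be read as evidence that more discussion prevents relapse. Part or all of it could instead reflect reachability. Restricting the model to the WhatsApp arm and choosing a single participation index would not remove this.

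**Working it through.** **The plan's own figure.** With 15% vs 23%, two-sided 5% and 90% power, pooled variance (mean rate 0.19):

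n per arm = [1.960·√(2·0.19·0.81) + 1.2816·√(0.15·0.85 + 0.23·0.77)]² / 0.08² = (1.087 + 0.707)² / 0.0064 ≈ 503.3, so 504 per arm and 1,008 in total. The stated size reproduces.

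**Inputs for the check.**
- WhatsApp arm of 504 and coded abstinence of 23% overall (Sample size calculation).
- Silent share 25% (pilot, section b), so 126 silent and 378 posting members.
- True abstinence t is the same in both strata (no real association).
- Ascertainment, meaning the share of true abstainers who are reached and validated, averages a and differs by d between strata. Both a and d are assumptions.
- One anchor for a: in the pilot WhatsApp arm 64% self-reported abstinence and 26% were validated, and 26/64 = 0.406. This is a lower bound on test uptake, because the unvalidated 59% may include failed tests as well as untested claimants.

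**Formulas.** t = 0.23/a. Ascertainment is a + 0.25d in posters and a − 0.75d in silent members. Coded rate = t × ascertainment. False support is the chance of a significant result in the hypothesised direction (nominal 2.5%), approximately Φ(ln OR/SE − 1.96), with SE² = 1/[378·p₁(1−p₁)] + 1/[126·p₀(1−p₀)].

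| a | t | d | Ascertained, posters / silent | Coded rate, posters / silent | OR | False support |
|---|---|---|---|---|---|---|
| 0.75 | 0.307 | 0.10 | 0.775 / 0.675 | 23.8% / 20.7% | 1.19 | about 10% |
| 0.75 | 0.307 | 0.20 | 0.80 / 0.60 | 24.5% / 18.4% | 1.44 | about 29% |
| 0.406 | 0.566 | 0.10 | 0.431 / 0.331 | 24.4% / 18.8% | 1.40 | about 25% |
| 0.406 | 0.566 | 0.20 | 0.456 / 0.256 | 25.8% / 14.5% | 2.05 | about 75% |

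In the last row the approximation gives 73% and simulation 75% to 77%. A separate GEE simulation (50 groups of 10, true abstinence 30%, ascertainment 80% vs 60%) gave OR 1.46 and 28% rejection. With equal ascertainment (80% in both) it gave OR 1.00 and 6% two-sided rejection.

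**When the coding does no harm.** Suppose 15% of active and 35% of inactive members are lost (assumed), and 27% of those reached are abstinent. The coded rates are 0.85·0.27 = 0.2295 and 0.65·0.27 = 0.1755, OR 1.40. The true OR is also 1.40 if none of the lost are abstinent, 1.21 if 10% are, and 1.00 if 27% are.

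**Why dropping unascertained cases is not a remedy.** Only claimants are tested; those who report smoking on the telephone need no sample. If everyone is reached by telephone and the gap arises at testing, a complete-case analysis keeps all smokers and drops untested quitters. Its odds are t·u/(1 − t), where u is uptake, so its OR equals the ratio of uptakes. At a = 0.406 that is 0.431/0.331 = 1.30 and 0.456/0.256 = 1.78, with about 16% and 49% false support.

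**The case against.** A reader might infer that the coding builds the association in. The documents do not support that. Two conditions are needed: ascertainment must differ by participation, and some of those missed must be abstinent. The documents give no figure for either. With equal ascertainment the artefact vanishes, and if everyone missed is smoking the coded result is correct.

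A reader might also take the pilot's 41% as the ascertainment rate. It is only a lower bound on test uptake: someone who failed the test is a known smoker, not a missing outcome. The lower two rows of the table are therefore an extreme case for test uptake.

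Further points stand:

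- The written rule covers those lost or refusing follow-up. That untested claimants are also counted as smokers is an inference from the validated outcome, and hypothesis 2 does not name its outcome.
- Posts received depend largely on the group, so that measure is less exposed than posts made or viewed.
- The pilot's silent quarter arose where some groups had only 2 to 5 members; this trial plans about 10.
- Multiple imputation is already planned, although nothing applies it to this model.
- Hypothesis 2 is secondary and observational.

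These points limit the claim to a risk of unknown size. They do not remove it, because the plan has no analysis that would reveal or bound it.

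**Conclusion.** The concern holds as a possible inflation of hypothesis 2, not as a certain one. With no true link, assumed gaps of 10 to 20 points give coded odds ratios of about 1.2 to 1.4 at 75% average ascertainment and about 1.4 to 2.05 at 41%. These figures rest on the assumed gaps, the pilot's 25% silent share, and equal true abstinence in both strata. As planned, a positive hypothesis 2 could not separate relapse prevention from ease of follow-up. The change is a cheap improvement that affects how a secondary result may be read. It does not bear on the randomised primary comparison or the sample size.

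**What to change.** For hypothesis 2 only, amend the analysis section to:

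1. Name the outcome, and fit the participation model in the WhatsApp arm.
2. Report the model with missing coded as smoking and, beside it, with multiple imputation or inverse-probability weighting. Treat 12-month call response and test uptake among claimants as separate steps, and include self-reported status, post counts and baseline predictors.
3. Not rely on a complete-case analysis.
4. Show self-reported 7-day abstinence beside validated abstinence.
5. Report call response and test uptake by participation level.
6. Add a missing-not-at-random range for abstinence among those missed.
7. Claim support for hypothesis 2 only if the association holds across these analyses.

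The cost is some wording and a little more analysis; no new data are needed. Intervals will be wider, and the imputed or weighted results rest on a missing-at-random assumption, which item 6 is there to test.

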This is a 2-arm open-labelled pragmatic randomized controlled trial, by comparing the 12-month tobacco abstinence between the recent quitters who will join WhatsApp group discussion (Intervention group) and those who will not (Control group). A 1:1 allocation will be used. The intervention content for both trial arms in the proposed trial will be the same and based on the US practice guidelines for smoking cessation[18], therefore the intervention effects due to the treatment content will be the same in both groups. Only the intervention platform (WhatsApp vs text messaging service) and the communication mode (one-way vs interactive) will be different between the 2 groups. This trial will be a pragmatic effectiveness trial to examine the effect of our intervention delivered under a real-life setting. We will apply less stringent eligibility criteria for the subjects, unobtrusive measurement on adherence, and include all subjects in the final analysis regardless of intervention compliance of each subject. The study design and recruitment setting were similar to our pilot RCT, which obtained ethics approval from the Institutional Review Board of the University of Hong Kong/Hong Kong Authority Hong Kong West Cluster (IRB reference no. UW-13-528) (Appendix 3).

Setting

The recruitment sites will be in all smoking cessation clinics under Hospital Authority (n=16), Tung Wah Group of Hospitals (n=6) and Pok Oi Hospital (n=8), which are the major smoking cessation service providers in Hong Kong offering free behavioural and pharmacological interventions. According to the record from Department of Health, the number of clients who attended smoking cessation clinic in the three service providers was 6,419, 2,756 and 1,380 per year, respectively. The 6-month quit rate (by intention-to-treat) of these services was ranged from 30 to 40%, and we expect the quit rate at earlier follow-up would be greater. These records, together with 55.1% recruitment rate from our pilot RCT, support that our proposed RCT can recruit sufficient participants (n=1,008) within our recruitment period (about 7 months). The representative from the Tung Wah Group of Hospitals is one of the co-A, and the other 2 service providers have already agreed to support this RCT (Appendix 4 & 5).

Procedures

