To ensure quality assurance and intervention fidelity, all moderators will be provided a training of smoking cessation knowledge, and moderating skills to motivate participants to share. Our co-investigator ([name] [name]), who has the experience of using Positive Psychology theories in the FAMILY project, will train the moderators to use specific texts, “emoji” and short videos to express gratitude and appreciation towards participants’ sharing. Also, a research nurse will review the discussion contents, provide service referral for the participants who relapse, and organize case conference with the moderators each month to improve group moderation skills.

The control group will only receive 3 mobile phone text messages each week in the 8 weeks after recruitment. These message contents will be the same as those received by the intervention group. Our intervention will not interrupt the services that all participants will be receiving in the cessation clinics.

Follow-up

All participants will be followed up via telephone by an allocation-blinded interviewer at 3-, 6- and 12-month after the random group allocation. Only the participants who report abstinence in the past 7 days will be invited to provide samples of exhaled breath and/or saliva for biochemical validation at their residence, workplace or nearby, as preferred by the quitters. The Bedfont Smokerlyzer and iScreen OFD Cotinine Saliva Test Kit will be used for validations. To increase participation, the participants will be given HK\$100 (approximately equivalent to US\$12.8) as a compensation for their time cost. All participants will not know the validation incentive at baseline. The validation takes very short time (3 minutes) and is easy.

Allocation concealment

All recruitment staff and participants will be concealed to the group allocation at recruitment. The research staff will open the envelope of group allocation according to the serial number on the envelope, so he/she will not know the group sequence.

Blinding

Participants and group moderators cannot and will not be blinded to the intervention. Assessors of the follow-up outcomes and the research analysts will not be involved in the recruitment and intervention delivery, and will be blinded to the group allocation (single blindness).

Outcomes

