 - 800 hours x 112 per hour incl. MPF /5 staff /9 months =\$1991 per staff per month
 - Total amount = \$1991 per month incl. MPF x 5 staff x 9 months = \$89,595
3. A part-time Registered Nurse (pt3, Nurse) with rich experience in smoking cessation:

- design intervention guidelines and the self-help booklet, providing training workshop to the recruitment staff and moderators (40 hrs x 2 months =80hrs)
 - hold case conference with the moderators, recruitment staff and telephone interviewers each month (4 hrs x 19 months =76hrs)
 - 80 hrs + 76 hrs x \$167 per hour incl. MPF /21 months=\$ 1241 per staff per month
 - Total amount = \$1,241 per month incl. MPF x 21 months =\$26,061
4. 10 part-time Student Research Assistants/ Technical Assistants (pt 2, Student RA/TA):
- Recruitment for subjects in clinics (4 hrs x 5 times per week x 30 weeks = 600 hrs)
 - Telephone follow-ups at 6-month and 12-month: 1,008 participants x 15 minutes x 2 follow-ups = 504 hrs;
 - Exhaled carbon monoxide (CO) validation at 6-month and 12-month: 504 intervention group participants x 23% quit rate = 116 participants; 504 control group participants x 15% quit rate = 76 participants, total: 192 quitters x 2 validations x 2 hrs = 768 hrs;
 - Total hours = 600hrs +504 hrs + 768 hrs = 1,872 hours
 - 1,872 hours x \$69 per hour incl. MPF / 10 staff / 19 months = \$680 per staff per month
 - Total amount =\$680 per month incl. MPF x 10 staff x 19 months = \$129,200

General Expenses - \$ 271,420

1. Conference (i.e. Travel and subsistence) (\$10,000)
2. Publication costs (\$20,000)
3. Audit fee (\$5,000)
4. Incentives for participants
Incentives for quitters who complete the exhaled CO validation at the 6-month and 12-month follow-ups: 504 intervention group participants x 23% quit rate = 116 participants; 504 control group participants x 15% quit rate = 76 participants, total: 192 quitters, 192 quitters x 2 validations x \$100 cash incentive = \$38,400
5. Incentives for participants who complete the telephone follow-up (1,008 participants x 2 follow-ups x \$50 supermarket coupon = \$100,800)
6. Incentive for participants who complete the in-depth interview (20 participants x \$300 = \$6,000)
 - Total = \$38,400 + \$100,800 + \$6,000 = \$145,200
7. Production of self-help booklet (1,100 booklets x \$5 = \$5,500)
8. Mobile phones for WhatsApp social group (3 phones x \$1,000 = 3,000)
9. CO monitors and mouthpieces for the validations (3 monitors x \$6000 = \$18,000)

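### The only missing-data sensitivity analysis imputes exhaled CO, which at 12 months is measured only in claimed quitters, so it cannot test the missing-equals-smoker rule

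*Combined protocol and SAP*

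**What the plan says.** Under *Follow-up* (section d(ii)), participants are telephoned at 3, 6 and 12 months, and "Only the participants who report abstinence in the past 7 days will be invited to provide samples of exhaled breath and/or saliva". Under *Outcomes*, the primary endpoint is 12-month abstinence confirmed by CO below 4 ppm, by saliva cotinine below 10 ng/ml, or by both.

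Under *Statistical analysis* (section d(iv)), participants who are lost or refuse follow-up count as smokers. The next sentence is the only missing-data sensitivity analysis: "The analysis with multiple imputation (MI) procedure to impute the missing exhaled CO will be conducted as sensitivity analysis". It does not state whose CO counts as missing, which predictors are used, whether self-reported status enters, or how a participant validated by saliva alone is handled. The other sensitivity analyses, under *Cost-effectiveness analysis*, vary the economic model's parameters.

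The budget (section f, staff item 4) sizes the validation work as "total: 192 quitters x 2 validations x 2 hrs = 768 hrs".

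**The concern.** Multiple imputation learns the distribution of a variable from the people in whom it was observed. Here those people were selected because they said they were not smoking. For someone lost to follow-up, the main unknown is whether they smoke. A CO model skips that question and goes straight to a value typical of a claimed abstainer.

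The stakes are visible in the pilot (section b). Self-reported abstinence was 64% vs 39% and validated abstinence 26% vs 15%. The gaps are 64 − 26 = 38 points and 39 − 15 = 24 points, so they differ between arms by 14 points, against a design effect of 23 − 15 = 8 points. How unvalidated participants are handled can therefore outweigh the effect the trial is sized to detect, and this sentence is the only planned check on that handling.

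**Working it through.** **1. The plan's own figure.** For 23% vs 15%, two-sided 5%, 90% power and 1:1 allocation, with pooled variance under the null:

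n = [1.960·√(2·0.19·0.81) + 1.282·√(0.23·0.77 + 0.15·0.85)]² / 0.08² ≈ 503.3, so 504 per arm and 1,008 in total. This matches the *Sample size calculation*.

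**2. How much CO is missing.** The budget takes 504 × 23% ≈ 116 and 504 × 15% ≈ 76, so 192 tested per round. CO is absent in 1,008 − 192 = 816, or 81%. The budget equates tested with validated and so allows for no failed tests. With pass rates of 90% or 80%, 192 validated would need 192/0.9 ≈ 213 or 192/0.8 = 240 tested, and CO would be absent in 79% or 76%.

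**3. What a CO model can learn.** Among participants with a 12-month CO value, 12-month self-report is constant, so its effect cannot be estimated. Baseline CO (suggested by the mouthpiece item in section f) would not help much, because everyone is abstinent at entry.

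**4. What the sentence could produce.** Let *s* be the share of all randomised participants in an arm who are reached and report abstinence, *L* the share lost, and *p* the share of tests passed. Assumptions not in the documents: *p* = 80–90%, *L* = 10–30%, both equal across arms, and *s* either at the pilot's 6-month rates (64% vs 39%) or at a low case (45% vs 37%).

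| Who is imputed | Rate per arm | *s* = 64% vs 39% | *s* = 45% vs 37% |
|---|---|---|---|
| A. Everyone untested, known smokers included | *p* | 80–90% in both; difference 0 | same |
| B. Untested abstainers only | *ps* | 51–58% vs 31–35%; 0.20–0.23 | 36–41% vs 30–33%; 0.06–0.07 |
| C. As B, with self-report imputed first for losses | *ps*/(1 − *L*) | 57–82% vs 35–50%; 0.22–0.32 | 40–58% vs 33–48%; 0.07–0.10 |
| D. As B, with losses given the testers' pass rate | *p*(*s* + *L*) | 59–85% vs 39–62%; 0.20–0.23 | 44–68% vs 38–60%; 0.06–0.07 |

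Example for D: 0.8 × (0.64 + 0.10) = 0.592 and 0.9 × (0.64 + 0.30) = 0.846. If *p* is 90% in one arm and 80% in the other, A gives +0.10 or −0.10.

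D is what direct imputation of CO for losses amounts to. It credits lost controls with 80–90% validated abstinence, where C gives 35–50% for responders in the same arm (pilot self-report rates).

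**5. Simulation check** (400 trials, 20 imputations, 504 per arm). The rates agree with the formulas to within about a point (the top of D came out at 84%). A rejected the null in 4–7% of trials, against the planned 90%. In the low case, B rejected in 46–63%.

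**6. Lower pass rates.** The pilot ratios, 26/64 = 0.41 and 15/39 = 0.38, do not separate untested abstainers from failed tests. If every abstainer had been tested, these would be the pass rates, and A would give 41% vs 38%, still close to no difference.

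**The case against.** The strongest reply is that known smokers are not in scope. The imputation sentence follows directly on the rule for participants who are lost or refuse. Self-reported smokers are never invited for a sample, so their CO is not applicable and their status is known. On that reading the target is untested abstainers, perhaps with losses, and the arm difference persists. The 80–90% under reading A also restates the assumed pass rate and is not an independent finding. Status at 3 and 6 months, and 6-month validation, could serve as predictors. The plan does not say cotinine results are discarded. Self-reported abstinence is a secondary outcome that does not depend on test uptake. And this is only a sensitivity analysis.

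Most of this stands. A reader might infer that the plan turns smokers into quitters and erases the treatment effect. The documents do not support that: nowhere do they say that smokers' CO will be imputed, and the difference vanishes only under reading A with equal pass rates.

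The reply does not remove the problem for losses. Earlier status can enter the model, but its relation to 12-month CO is still estimated only among people who claim abstinence at 12 months. The self-report outcomes do not resolve loss to follow-up either.

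**Conclusion.** The point holds at moderate severity. CO is the wrong variable to impute, because every observed 12-month value comes from a claimed quitter, and the target set and model are undefined. Depending on an unstated choice, one sentence supports differences from −0.10 to 0.32, around a design effect of 0.08. An analysis with that spread cannot show whether the missing-equals-smoker result is robust.

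The direction of any distortion in the arm difference is not established. What is firm, once losses are imputed directly on CO, is inflation of the abstinence rates. The sizes rest on the assumed pass, loss and low-case self-report rates and on carrying the pilot's 6-month self-report to 12 months. The 81% rests on the budget alone.

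A reader might also infer that the primary result is compromised. It is not: the primary rule, estimate and sample size are untouched.

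**What to change.** Replace imputation of CO with multiple imputation of the binary validated endpoint:

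1. Keep participants who report smoking at 12 months as not abstinent.
2. For those lost at 12 months, impute 12-month self-report by arm from 3- and 6-month status and baseline predictors. Use WhatsApp group, if at all, only within the intervention arm, since controls have none.
3. For observed or imputed self-reported abstainers with neither a CO nor a cotinine result, impute confirmed or not confirmed by arm from those tested. Count cotinine-only results as observed.
4. Steps 2 and 3 still assume missing at random, and step 3 still borrows from those who accepted testing. Add an arm-specific delta shift to both, ranging as far as missing equals smoker, and report the tipping point.

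The cost is plan wording and some programming, with no new data. The change should be made before the 12-month outcomes are analysed.

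### No primary analysis of 12-month validated abstinence is designated, and the only cluster-adjusted model is labelled post-hoc

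*Combined protocol and SAP*

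**What the plan says.** All references are to the combined protocol and SAP.

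- **Design and Randomization.** Participants are randomized individually, and "A 1:1 allocation will be used".
- **Interventions.** Intervention participants are then placed in about 50 WhatsApp groups of 10, a few of 11, for 8 weeks. Controls receive individual text messages. Clustering therefore arises in one arm only.
- **Sample size calculation.** The trial is sized "To detect a significant difference of quit rate with 2-tailed z-test", and the result is that "we will need 1,008 participants in total (504 participants per group". No ICC or design effect appears.
- **Statistical analysis.** The section acknowledges correlated outcomes within a WhatsApp group and gives this as the reason that "a post-hoc analysis by generalized estimating equation (GEE) model will be used to summarise the intervention effect with the odds ratios", with and without baseline adjustment. Counts of posts are later added to what it calls the final GEE model. The number needed to treat is "computed by taking the reciprocal of the risk difference between the 2 RCT groups".

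No sentence in the Statistical analysis section says which analysis tests the primary hypothesis.

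**The concern.** The plan recognises a dependence between outcomes and then gives the model that respects it a label normally reserved for supplementary work. The only test it names elsewhere treats all participants as independent. A team could therefore decide the primary hypothesis on an unadjusted comparison, treat a less favourable GEE as secondary, and still be within the plan.

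The choice is also open within the GEE itself. The plan lists unadjusted and adjusted versions, and a version with post counts, which are measured after randomization. None is named as primary.

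Correlation is plausible. The intervention works through group discussion and peer support, and the Background reports that small pilot groups led to inactive discussion. If outcomes vary between groups, an unadjusted interval is too narrow and an unadjusted p-value too small.

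**Working it through.** **Reproducing the plan's figure.** Inputs from the Sample size calculation are 23.0% against 15.0%, two-sided 5%, and 90% power. With pooled variance, mean rate 0.19 and no continuity correction:

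n per arm = [1.960 × √(2 × 0.19 × 0.81) + 1.2816 × √(0.23 × 0.77 + 0.15 × 0.85)]² / 0.08² = [1.0874 + 0.7073]² / 0.0064 = 503.3, rounded up to 504.

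The total of 1,008 reproduces exactly, so the calculation contains no allowance for clustering.

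**Type I error of an unadjusted z-test.** The group size m = 10 comes from the Interventions section. The ICC is my assumption, taken from 0 to 0.10, because the documents give none.

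- Design effect in the intervention arm: DE = 1 + (m − 1) × ICC. In the control arm it is 1.
- With equal arms and equal rates, the true variance divided by the assumed variance is VR = (DE + 1)/2.
- True two-sided type I error = 2 × [1 − Φ(1.96/√VR)].
- Proportion by which the standard error is understated = 1 − 1/√VR.

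Example at ICC 0.05: DE = 1 + 9 × 0.05 = 1.45; VR = 2.45/2 = 1.225; 1.96/√1.225 = 1.771; type I error = 0.0766.

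**Power of a cluster-adjusted test at 504 per arm.** Let SE₀ = √[0.19 × 0.81 × (DE + 1)/504] and SE₁ = √[(0.23 × 0.77 × DE + 0.15 × 0.85)/504]. Power = Φ[(0.08 − 1.96 × SE₀)/SE₁].

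Example at ICC 0.02: SE₀ = 0.02580, SE₁ = 0.02584, and Φ(1.139) = 0.873.

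| Assumed ICC | DE | VR | SE understated by | Type I error, formula | Type I error, simulated | Power, adjusted test | Total N for 90% |
|---|---|---|---|---|---|---|---|
| 0 | 1.00 | 1.000 | 0% | 5.0% | 5.0% | 90.0% | 1,008 |
| 0.01 | 1.09 | 1.045 | 2.2% | 5.5% | 5.4–5.5% | 88.7% | 1,056 |
| 0.02 | 1.18 | 1.090 | 4.2% | 6.1% | 6.0–6.1% | 87.3% | 1,104 |
| 0.05 | 1.45 | 1.225 | 9.6% | 7.7% | 7.6% | 83.0% | 1,248 |
| 0.10 | 1.90 | 1.450 | 17.0% | 10.4% | 10.4% | 76.3% | 1,490 |

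The simulated column uses a beta-binomial model with 46 groups of 10 and 4 of 11 (504 in all) against 504 independent controls. It was run with 200,000 replicates at each of two event rates, 15% and 19%. The power column is a normal approximation without a small-sample correction.

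**The case against.** A reader might infer that the z-test is the confirmatory analysis and that the plan therefore inflates type I error. The documents do not support this. The z-test appears only where the trial is sized, and the Statistical analysis section neither mentions it nor assigns it to the outcome. The GEE is the only model named for the treatment effect. It is written in advance and its stated reason is the clustering, so the label may be loose wording. If the GEE is primary and correctly specified, the inflation disappears and the consequence is lost power instead.

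The size of the inflation is also conditional. The outcome is at 12 months and the groups last 8 weeks, so the ICC may be small. Randomization is individual and groups form afterwards. If group membership affects nobody's outcome, an independent test keeps approximately its 5% level. Inflation needs an average effect of zero with groups that truly differ. At a 15% rate, ICC 0.05 means a between-group standard deviation of √(0.05 × 0.15 × 0.85) = 8 percentage points, and ICC 0.10 means 11. The upper figures therefore require large, offsetting group effects.

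Two further inferences fail. The number needed to treat is not shown to be wrong: the plan describes a point estimate, and clustering with nearly equal groups does not bias a simple difference in proportions. Silence on how controls are coded in the GEE is missing detail, not a contradiction.

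These objections limit the claim without removing it. If the label is a slip, the text still has to change, because the primary analysis remains undesignated. The narrow interval also does not depend on the null: if the intervention works and groups vary, unadjusted precision is still overstated.

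**Conclusion.** The concern holds as a failure to designate the primary analysis. The plan concedes within-group correlation, labels the only model that handles it post-hoc, and leaves open a decision on an unadjusted test. It does not establish that such a test will be used.

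If one is used, true type I error runs from 5% at ICC 0 to about 5.5% at 0.01, 6.1% at 0.02, 7.7% at 0.05 and 10.4% at 0.10. The effect is modest at small ICCs, partly because only one arm is clustered. These figures rest on assumed ICCs, groups of 10, equal arms, independent controls, and a null in which groups differ around a mean effect of zero.

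**What to change.** Before unblinded outcomes are analysed, revise the Statistical analysis section as follows:

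1. Delete the post-hoc label and name one primary analysis of 12-month validated abstinence: a GEE or an equivalent partially nested model, without post counts. State whether the version with or without baseline adjustment is primary.
2. Define the clusters. Each WhatsApp group as formed at allocation is one cluster, including members who later leave. Each control is a cluster of size 1.
3. Specify robust standard errors with a small-sample correction for about 50 groups.
4. Report any unadjusted z-test as descriptive only. Take any interval for the risk difference from the cluster-adjusted model.
5. Keep the models with post counts as separate, secondary analyses of participation.
6. State the assumed ICC and restate power at 1,008 participants.

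The change is one of wording and needs no new data. It costs a wider interval and power below the stated 90%: about 88.7%, 87.3%, 83.0% and 76.3% at ICC 0.01, 0.02, 0.05 and 0.10. The sample size calculation already omits this loss, and the change makes it visible.
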